## 20. STATISTICAL METHODOLOGY

### 20.1 General Methodology

The Mixed-Effect Model Repeated Measure (MMRM) will be the primary analysis for the primary efficacy endpoint (MADRS change from baseline); an unpaired t-test will be a secondary analysis. The proportional hazard model (PHREG) will be the primary analysis for time to event endpoints (time to remission, time to discontinuation); the unstratified log rank test will be a secondary analysis. The MMRM and PHREG models will all include treatment and the following four baseline covariates:

- sex
- mood stabilizer use
- anti-psychotic use
- evidence of suicide event in their lifetime.

All primary analyses will be in the mITT population as primary and repeated in the Per Protocol population if >5 percent are excluded.

All of the instruments used to measure SSIB or depression constitute serial continuous and ordinal outcomes that will be analyzed using MMRM with LOCF to account for missing data and early discontinuations. The models will include treatment group, study visit, the interaction between study visit and treatment group, the baseline level of the variable being analyzed, and the above four pre-defined baseline stratification factors as fixed effects. The primary endpoint change from baseline MADRS-10 will be analyzed using the MMRM model which will include baseline MADRS; treatment group; study visit; study visit\*treatment; sex, mood stabilizer use, anti-psychotic use, and evidence of suicide event in their lifetime as defined above. An unstructured error structure will be assumed.

SAS PROC MIXED will be used for continuous endpoints.

In addition, supportive analyses will be performed using multiple imputation which will be performed to address any missing data. The method of Little and Rubin will be used. The presentation of the results for the primary efficacy endpoints using the ITT population will be based on the observed data with multiple imputation for missing endpoint data using SAS PROC MI. Missing data will be imputed using MCMC imputation under the assumption of a missing at random using the mITT population. The SAS® procedure PROC MI will be used for the MCMC imputation of 25 complete data sets.

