16.3.3 Key Secondary Hypotheses

The key secondary hypothesis are that:

- treatment with NRX-101 is superior to lurasidone in improving symptoms of suicidality as measured by the CGI-SS over 6 weeks of treatment. The null hypothesis for the primary endpoint is the mean change from baseline of CGI-SS for NRX-101 is greater than or equal to the mean change from baseline of CGI-SS for lurasidone while the alternative hypothesis is that the mean change from baseline of CGI-SS is less than the mean change from baseline of CGI-SS for lurasidone (improvement). Baseline is defined as CGI-SS score at this study entry.
- that NRX-101 is superior to lurasidone in time to treatment failure as defined as: study discontinuation due to Adverse Events; psychiatric hospitalization; or requiring a change in antidepressant treatment. Time to treatment failure may be ascertained as the treating physician's determination of a study discontinuation due to lack of efficacy; withdrawal due to a treatment related adverse event a psychiatric hospitalization; or the patient requiring any change in their baseline antidepressant, mood stabilizer, or antipsychotic medication. Titration or change in timing of administration of study medication will not be considered a failure of therapy. Lack of efficacy is defined as the need to implement a new treatment plan or an increase in suicidal ideation (a score of 4 or 5 on the C-SSRS, emergent suicidality requiring hospitalization), or increase in depressive symptoms (a score increase of \geq 5 for two consecutive visits on the MADRS total score). The need to implement a new treatment plan includes the addition of new antidepressant medication or somatic treatment (e.g. ECT or rTMS treatment) or an escalation of care such as hospitalization (i.e. moving the patient from outpatient care to initiating inpatient, partial or day hospitalization). Time to failure will be assessed using a Kaplan-Meier lifetable. The formal hypothesis test will be to detect a 0.421 hazard ratio (HR) with 80% power for a two-sided test using a proportional hazard model; a 0.545 hazard ratio reaches two-sided p=0.05.

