16.8.5 General Methodology

The Mixed-Effect Model Repeated Measure (MMRM) will be the primary analysis for the primary efficacy endpoint (MADRS change from baseline); an unpaired t-test will be a secondary analysis. The proportional hazard model (PHREG) will be the primary analysis for time to event endpoints (time to relapse, time to discontinuation); the unstratified log rank test will be a secondary analysis. The MMRM and PHREG models will all include treatment and the following four baseline stratification factors:

- sex
- mood stabilizer use
- anti-psychotic use
- evidence of suicide event in their lifetime.

All primary analyses will be in the ITT population as primary and repeated in the Per Protocol population if >5 percent are excluded.

All of the instruments used to measure SSIB or depression constitute serial continuous and ordinal outcomes that will be analyzed using MMRM with LOCF to account for missing data and early discontinuations. The models will include treatment group, study visit, the interaction between study visit and treatment group, the baseline level of the variable being analyzed, and the above four pre-defined baseline stratification factors as fixed effects. The primary endpoint change from baseline MADRS-10 will be analyzed using the MMRM model which will include baseline MADRS; treatment group; study visit; study visit*treatment; sex, mood stabilizer use, antipsychotic use, and evidence of suicide event in their lifetime as defined above. An unstructured error structure will be assumed.

SAS PROC MIXED will be used for continuous endpoints and PROC GENMOD will be used for binary endpoints.

In addition, multiple imputation will be performed to address any missing data. The method of Little and Rubin will be used. The presentation of the results for the primary efficacy endpoints using the ITT population will be based on the observed data with multiple imputation for missing endpoint data using SAS PROC MI. Missing data will be imputed using MCMC imputation under the assumption of a missing at random using the ITT population. The SAS® procedure PROC MI will be used for the MCMC imputation of 25 complete data sets.

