### 16.3 Secondary Hypotheses

The secondary hypothesis are that:

- treatment with NRX-101 is superior to lurasidone in improving symptoms of suicidality as measured by the CGI-SS over 6 weeks of treatment. The null hypothesis is the mean change from baseline of CGI-SS for NRX-101 is greater than or equal to the mean change from baseline of CGI-SS for lurasidone while the alternative hypothesis is that the mean change from baseline of CGI-SS is less than the mean change from baseline of CGI-SS for lurasidone (improvement). Baseline is defined as CGI-SS score at this study entry.
- that NRX-101 is superior to lurasidone in time to treatment failure as defined as: study discontinuation due to Adverse Events; psychiatric hospitalization; or requiring a change in antidepressant treatment. Time to treatment failure may be ascertained as the treating physician's determination of a study discontinuation due to lack of efficacy; withdrawal due to a treatment related adverse event a psychiatric hospitalization; or the patient requiring any change in their baseline antidepressant, mood stabilizer, or antipsychotic medication. Titration or change in timing of administration of study medication will not be considered a failure of therapy. Lack of efficacy is defined as the need to implement a new treatment plan or an increase in suicidal ideation (a score of 4 or 5 on the C-SSRS, emergent suicidality requiring hospitalization), or increase in depressive symptoms (a score increase of  $\geq 5$  for two consecutive visits on the MADRS total score). The need to implement a new

treatment plan includes the addition of new antidepressant medication or somatic treatment (e.g. ECT or rTMS treatment) or an escalation of care such as hospitalization (i.e. moving the patient from outpatient care to initiating inpatient, partial or day hospitalization). Time to failure will be assessed using a Kaplan-Meier lifetable. The formal hypothesis test will be to detect a 0.421 hazard ratio (HR) with 80% power for a two-sided test using a proportional hazard model; a 0.545 hazard ratio reaches two-sided  $p=0.05$ .

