### 20.2 Other Time to Event Efficacy Endpoints

Other time-to-event outcomes (all-cause discontinuation, and time to remission) further characterize this multi-component disorder. Time to event is a more sensitive measure than an assessment at a fixed time. Time to such events will be displayed using a Kaplan-Meier lifetable,

with the treatment groups compared using two-sided unstratified log rank tests (secondary) and a proportional hazard model (primary) to include the above cited baseline covariates.

Treatment Failure will be centrally judged blind in real time by the study physician using baseline measures of depression and suicidality as a guide. Treatment failure is defined above.

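### The Cox model for time to treatment failure leaves out baseline C-SSRS level and baseline MADRS; adding both is a cheap efficiency gain, not a correction of an error

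*SAP*

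**What the plan says.** SAP 18.3 tests MADRS first, CGI-SS second and time to treatment failure third, each at two-sided 0.05. For the third, SAP 16.3 plans to "detect a 0.421 hazard ratio (HR) with 80% power for a two-sided test using a proportional hazard model", and Protocol 16.3.3 adds that "a 0.545 hazard ratio reaches two-sided p=0.05". Neither document states the number of failures assumed.

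SAP 20.1 fixes the covariates: "The MMRM and PHREG models will all include treatment and the following four baseline covariates". The list is sex, mood stabilizer use, anti-psychotic use and lifetime suicide event. Protocol 16.8.5 gives the same list under another label: "The MMRM and PHREG models will all include treatment and the following four baseline stratification factors". SAP 20.2 repeats it for the other time-to-event outcomes, with "a proportional hazard model (primary) to include the above cited baseline covariates".

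For the serial scales, SAP 20.1 goes further and includes "the baseline level of the variable being analyzed, and the above four pre-defined baseline stratification factors as fixed effects". That sentence also lists visit and visit-by-treatment terms, so it describes the MMRM and not the Cox model.

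Failure is a composite (SAP 16.3 and 17.1.2): discontinuation for lack of efficacy, withdrawal for a treatment-related adverse event, psychiatric hospitalization, or a change in baseline psychotropic medication. Lack of efficacy can be met by an increase in ideation, glossed as "a score of 4 or 5 on the C-SSRS, emergent suicidality requiring hospitalization", by a sustained MADRS rise, or by a new treatment plan. SAP 20.2 has a physician judge failure blind, "using baseline measures of depression and suicidality as a guide".

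**The concern.** The plan adjusts for baseline severity where the outcome is a scale score, but not where the outcome is an event partly triggered by the same scales. Entry is restricted to C-SSRS level 3 or 4 (SAP synopsis, Study Design). A participant entering at 4 already holds a score that the lack-of-efficacy wording names; one entering at 3 does not. Baseline level is therefore plausibly prognostic.

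The listed covariates do not replace it. Lifetime suicide event, and the randomization stratum of an event in the prior 12 months (SAP 14), describe history, not current ideation.

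If a prognostic covariate is left out of a Cox model, the treatment hazard ratio (HR) being estimated lies closer to 1 and power falls. A chance imbalance in that covariate then moves the estimate with nothing in the model to offset it. Both matter in a gated test with 37 per arm.

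**Working it through.** **1. The plan's own figures.** Inputs: HR 0.421, 80% power, two-sided 0.05, 1:1 allocation (SAP 16.3, 19.3 and 8).

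- Schoenfeld events = 4(1.960 + 0.842)² / (ln 0.421)² = 31.4 / 0.748 = 42.
- Power with 42 events = Φ(√42/2 × 0.865 − 1.960) = Φ(0.843) = 80%.
- Critical HR = exp(−2 × 1.960/√42) = 0.546, against 0.545 stated. Working back from 0.545 gives 41.7 events.

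The figures reproduce with 42 failures, that is 42/74 = 57% of participants.

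**2. Which model carries what.**

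| Term | MMRM | Cox, time to treatment failure |
|---|---|---|
| Four listed covariates | yes | yes |
| Baseline of the scale analysed | yes | no |
| C-SSRS level at Visit 2 | no, unless it is the scale analysed | no |
| MADRS at Visit 2 | yes, for MADRS | no |

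Both scales are rated at Visit 2 (SAP Table 1).

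**3. Effect on power.** The documents give no prognostic strength and no split between levels 3 and 4, so these inputs are assumed. The hazard is λ·exp(β·treatment + ln g₁·[level 4] + ln g₂·[MADRS in SD units]), with exp(β) = 0.421 conditional on the two scales. There are 37 per arm, half at each level, the four SAP covariates set as non-prognostic, and follow-up to the 42nd failure. Each row is 5,000 trials with a Wald test at 1.96; the simulation error of each power is about √(0.77 × 0.23/5000) = 0.6 points.

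| g₁ (level 4 vs 3) | g₂ (per SD) | Power, four covariates | Power, plus both | Gain (points) | Median HR, four / plus both |
|---|---|---|---|---|---|
| 1 | 1 | 77.0% | 76.2% | −0.8 | 0.41 / 0.40 |
| 1.5 | 1 | 76.4% | 77.0% | 0.6 | 0.41 / 0.39 |
| 1.5 | 1.25 | 74.6% | 76.6% | 2.0 | 0.42 / 0.40 |
| 2 | 1.25 | 72.5% | 76.9% | 4.4 | 0.43 / 0.39 |
| 3 | 1.25 | 69.0% | 77.8% | 8.8 | 0.45 / 0.39 |
| 3 | 1.5 | 65.2% | 76.7% | 11.5 | 0.46 / 0.39 |
| 4 | 1.5 | 58.8% | 76.9% | 18.1 | 0.49 / 0.39 |

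A separate simulation of the same design gave 77.5% vs 77.4% (row 1), 77.1% vs 77.1% (row 2), 72.1% vs 76.4% (row 4) and 67.3% vs 76.4% (row 5). The last two rows of the table show where strong assumptions lead; nothing in the documents supports values that large.

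**4. Chance imbalance.** With a 50/50 split, the SD of the between-arm difference in level-4 share is √(2 × 0.25/37) = 11.6 points. A difference of 15 points or more has probability 2[1 − Φ(0.15/0.116)], about 20%, and about 10% against NRX-101. In those adverse trials the four-covariate median HR rises from 0.43 to 0.47 (g₁ = 2, g₂ = 1.25) and from 0.45 to 0.55 (g₁ = 3, g₂ = 1.25). With both scales added it is 0.37 and 0.40. The critical HR is about 0.545.

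**5. Cost.** Events per parameter fall from 42/5 = 8.4 to 42/7 = 6.0, or to 42/6 = 7.0 if only C-SSRS level is added. With no treatment effect, Wald type I error was 5.6–6.3% with four covariates and 5.8–6.7% with both added; the largest gap in any scenario was 0.8 points.

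**The case against.** Several points on the other side stand.

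- A reader might infer that failure is defined by C-SSRS and MADRS. It is not. The scale thresholds sit inside lack of efficacy, and adverse-event withdrawal, hospitalization and medication change are separate routes. This weakens the expected prognostic effect.
- SAP 16.3 speaks of an increase in ideation. Read strictly, someone entering at 4 must reach 5 and someone entering at 3 must reach 4, so the head start goes. The MADRS trigger is a rise too, and judging failure against baseline makes the event partly baseline-relative already. Baseline level can still matter under that reading, but its strength and even its direction are then less predictable.
- The level split is unknown. SAP 8 describes participants answering yes to items 3 and 4, while inclusion criterion 10 says either or both. Under SAP 8 the covariate could be constant. The Visit 2 rating also uses the since-last-visit form, with a different look-back from screening.
- A reader might infer that the stated 80% power is missed because of the omission. That is not shown. The SAP does not say that 0.421 is conditional on C-SSRS level; as the HR in the planned model, it gives 80% with 42 events. In the simulation power is 77% even when neither scale is prognostic, and adding them reaches only 76–78%.
- Suicidality history is partly handled, through the lifetime event in the model and the 12-month event in the randomization.

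What the objection does not remove is the asymmetry. In these scenarios adjustment costs under 1 point of power at worst and may gain several.

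**Conclusion.** The omission is plain in both documents, but it is not an error. The four-covariate test is valid: leaving the scales out does not inflate type I error. The shift of the HR toward 1 reflects a different, less finely conditioned target, not bias in the planned estimate.

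The point is a cheap efficiency improvement to the third gated test. The gain in power is about zero with no or weak prognostic effect, and about 4 to 9 points with C-SSRS level HR 2 to 3 and MADRS HR 1.25 per SD. It rests on assumed prognostic strengths, an assumed even split between levels, and the 42 failures implied by the plan. The case for C-SSRS level is stronger than that for MADRS. The documents give no support for extending the change to time to discontinuation.

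**What to change.** Before unblinding, and decided by staff who have not seen the interim comparison, amend SAP 20.1 and 20.2 as follows.

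- Name time to treatment failure among the Cox endpoints; SAP 20.1 now gives only remission and discontinuation as examples.
- For that endpoint, add the Visit 2 C-SSRS ideation level (3 vs 4, if both levels are represented) and the Visit 2 MADRS total to the four covariates.
- Keep the four-covariate Cox model as a sensitivity analysis and the unstratified log-rank test as the secondary analysis.
- State the 42 failures assumed. Set in advance a failure count below which only C-SSRS level is added.

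The cost is SAP wording and one model statement, with no new data. The statistical price is two more parameters and a Wald type I error up to about 1 point higher.

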### 20.2 Other Time to Event Efficacy Endpoints

Other time-to-event outcomes (all-cause discontinuation, and time to remission) further characterize this multi-component disorder. Time to event is a more sensitive measure than an assessment at a fixed time. Time to such events will be displayed using a Kaplan-Meier lifetable,

with the treatment groups compared using two-sided unstratified log rank tests (secondary) and a proportional hazard model (primary) to include the above cited baseline covariates.

Treatment Failure will be centrally judged blind in real time by the study physician using baseline measures of depression and suicidality as a guide. Treatment failure is defined above.

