Statistical Methods:	
All randomized participants will be evaluated for depression (MADRS), suicidality (C-SSRS), and other efficacy endpoints while on the study. Analyses will be conducted under ICH E9 (R1) guidelines. C-SSRS is a safety endpoint.
 
Change from baseline in MADRS total scores through study exit to compare treatments will be analyzed using Mixed Model Repeated Measures analysis (SAS PROC MIXED) with Last Observation Carried Forward (LOCF) containing sex, baseline use of mood stabilizers, baseline use of anti-psychotics, BPRS rating scale (none, any) and evidence of a suicidal event in their lifetime (none, any) as stratification factors in the analysis. Additional analyses will alternatively rely on multiple imputation to assess the impact of dropouts. The NRX-101 and lurasidone treatment groups will be compared using stratified and unstratified log rank tests, as well as a proportional hazard model for time to relapse.

Sample Size Calculation:	Participants will be randomized in a 1:1 ratio (NRX-101:lurasidone). With 37 participants per group, there is an 80 percent power to detect a mean 8.85-unit advantage for NRX-101 vs lurasidone for the CFB to Day 42, assuming a SD of 13.4 for NRX-101 versus lurasidone at 6 weeks for a two-sided hypothesis test with two-sided 5 percent Type I error. This equates to a 0.66 effect size.
Interim Analysis	
Two interim analyses are planned. The first interim analysis (IA) assessing safety will be conducted six weeks after the first 30-35 participants have been followed for 6 weeks and the second IA assessing futility (primary efficacy endpoint) will be performed after the first 45-50 participants have reached 42 days post-randomization.
 
Each interim analysis has a different objective with neither interim analysis spending any Type 1 error. The study will be stopped at the first interim analysis if Serious Adverse Events are deemed statistically significantly more common in the NRX-101 group compared to the lurasidone group in a manner deemed by the DMC to pose a potential danger to human subjects. The study will be stopped at the second IA for futility if the conditional power (CP) is less than 10%. In the event that the study is not stopped for either safety or futility, then enrollment will continue until a total of 74 subjects are randomized. This preserves two-sided <math>p=0.05</math> for the final analysis.

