### **12.2.6.2 Suicidal Ideation and Clinical Management**

The documentation and proper management of suicidal ideation by sites will be documented with the use of the C-SSRS, completed by site clinicians during all visits. Safety will be evaluated throughout the course of the study.

Any patient who, based on the investigator's judgment, poses an imminent risk of suicide should be discontinued from the study. Suicide risk is assessed by the clinician at every visit.

Suicide, self-harm, and attempted suicide, irrespective of the method, will be reported as AEs (all suicides are SAEs; attempted suicides are considered to be SAEs). The event will be identified as suicide or attempted suicide, and the method of the suicide or attempt will be provided. If an attempted suicide meets the criteria for an SAE, the event must be reported according to the guidelines in Section 12.2.5. If a suicide attempt does not meet the criteria for an SAE, it will be considered a reportable AE, and a Suicidal Ideation or behavior Reportable Event Form will be completed by the investigator and submitted in accordance with the SAE reporting procedure in Section [12.2.5](#).

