### 18.2 Power and Significance

These sample size calculations are based on the alternative hypothesis corresponding to a 0.66 effect size which corresponds to a mean 8.85-unit MADRS-10 advantage change from baseline for NRX-101 vs control. A total of 74 subjects are to be randomized 1:1 to support the final analysis. As summarized below in Table 2, there is 80% power to detect a 0.66 effect size; a 0.462 effect size would reach two-sided  $p=0.05$ . A 0.462 (moderate) effect size reflects a 50 percent drop (based on lurasidone published data) in mean change from baseline for lurasidone with an assumed standard deviation of 13.4; this approximately corresponds to a -16 mean CFB for NRX-101 and a -10 mean CFB for lurasidone.

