### **19.3 Conventions**

Study visit dates will be analyzed using the nominal visit instead of the actual visit date.

Means, mean changes, standard deviations, and ranges will be presented separately for each treatment group. These endpoints will be evaluated using a paired t-test and between study treatment groups using an unpaired t-test at each time; these p-values will be presented as descriptive statistics.

For continuous variables, the mean, standard deviation, minimum, median and maximum will be presented, together with the total number of observations and the number of missing and non-missing values.

For ordinal and categorical variables, absolute and relative frequencies will be reported. Relative frequencies will be based on all observations and reported as percentages. Unless otherwise specified, percentages will be based on the number of participants with data and will not be calculated for missing categories.

Adverse events, medical histories, and concomitant medications will be reported on a patient and an event basis. Percentages will be calculated using the number of participants in the Safety population analysis set as the denominator.

All hypotheses will be tested at 5 percent (final analysis) level of significance using a two-sided test unless otherwise specified.

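### Time to remission has no rule for patients who discontinue before remitting; if they are censored by default, the Kaplan-Meier curve overstates the proportion who remit

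*SAP*

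**What the plan says.** SAP 20.1 states that the proportional hazards model "will be the primary analysis for time to event endpoints (time to remission, time to discontinuation"), with the unstratified log-rank test as secondary. SAP 20.2 opens: "Other time-to-event outcomes (all-cause discontinuation, and time to remission) further characterize this multi-component disorder". It repeats both tests with the baseline covariates and adds: "Time to such events will be displayed using a Kaplan-Meier lifetable". Remission and discontinuation are thus handled identically.

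Neither document gives a censoring rule for time to remission or mentions competing events or cumulative incidence. The LOCF convention in SAP 20.1 belongs to the MMRM. SAP 19.4 leaves intercurrent events to case-by-case adjudication at the data review meeting.

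Exits are partly driven by outcome. SAP 12.2.6.2 says that a patient who, in the investigator's judgment, "poses an imminent risk of suicide should be discontinued from the study". SAP 12.3.1 withdraws patients who need excluded medication. Under Protocol 9.1.3 a discontinuing patient has an early termination visit if possible and then moves to usual care. C-SSRS and MADRS are scheduled at that visit (SAP Table 1), and no efficacy visit follows it.

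The event is not fixed either. SAP 17.1.3 uses C-SSRS of 2 or less, held to the end of the study. SAP 17.1.4 uses MADRS of 10 or less at the last two visits. SAP 7.4 uses C-SSRS of 3 or less at Week 6. SAP 20.2 does not say which applies. The SAP synopsis labels remission from suicidality exploratory, and SAP 18.3 leaves it out of the hierarchy.

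**The concern.** A patient who leaves unremitted cannot be seen to remit afterwards. Censoring that patient at exit lets the Kaplan-Meier estimator assume the same later remission rate as in patients who stay. This is hard to defend for someone withdrawn for imminent suicide risk. One minus Kaplan-Meier then estimates remission in a setting where nobody leaves, not the share of randomized patients who remit.

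The trial itself expects exits to differ by arm: SAP 7.4 hypothesises fewer discontinuations on NRX-101 for lack of efficacy or worsening suicidality. If so, the two curves are inflated to different degrees, and a gain in remission that comes from keeping patients in the study would not show in the planned comparison.

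**Working it through.** **Plan figures.** No figure is given for time to remission. The stated primary calculation reproduces: "With 37 participants per group, there is an 80 percent power to detect a mean 8.85-unit advantage for NRX-101 vs lurasidone", "assuming a SD of 13.4 for NRX-101 versus lurasidone at 6 weeks", gives d = 8.85/13.4 = 0.660, and a two-sided 5% t-test with 37 per arm has 79.98% power. The critical effect size is 0.463 (stated 0.462). The time-to-failure hazard ratios in SAP 16.3 are also mutually consistent. By Schoenfeld, 4 × (1.96/ln 0.545)² = 41.7 events and 4 × (2.80/ln 0.421)² = 41.9 events, so both fit about 42 failures in 74 patients (57%).

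**Size of the overstatement.** Assumptions, none from the documents: constant hazards to Day 42, a proportion R remitting, and a proportion X exiting before remission. From the plan: 37 per arm.

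- Total cumulative hazard: Λ = −ln(1 − R − X)
- Remission part: Λr = Λ × R/(R + X)
- Kaplan-Meier reading with exits censored: 1 − exp(−Λr)
- Single-arm SE: √(R(1 − R)/37), which is 8.05 points at R = 40% and 7.53 at R = 30%

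Example, R = 40% and X = 20%: Λ = −ln 0.40 = 0.916; Λr = 0.916 × 2/3 = 0.611; 1 − exp(−0.611) = 45.7%; shift 5.7/8.05 = 0.7 SE.

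| True remission R | Exits X | 1 − KM | Shift (points) | Shift (SE) |
|---|---|---|---|---|
| 40% | 20% | 45.7% | 5.7 | 0.7 |
| 40% | 30% | 49.7% | 9.7 | 1.2 |
| 40% | 40% | 55.3% | 15.3 | 1.9 |
| 30% | 20% | 34.0% | 4.0 | 0.5 |
| 30% | 30% | 36.8% | 6.8 | 0.9 |
| 30% | 40% | 40.3% | 10.3 | 1.4 |

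The shift falls below half a single-arm SE when exits are under about 15% (R = 40%), 19% (R = 30%) or 25% (R = 20%).

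**Unequal exits, equal remission hazards.** Take 35% remission and 40% exits on lurasidone. Then Λ = −ln 0.25 = 1.386, Λr = 1.386 × 0.35/0.75 = 0.647 and the exit hazard is 0.739. As an illustration, multiply the exit hazard by 0.421 for NRX-101, giving 0.311. Its true remission is 0.647/0.958 × (1 − exp(−0.958)) = 41.6%. True remission is 35.0% against 41.6%, yet 1 − KM is 47.6% in both arms and the cause-specific hazard ratio is 1.

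**Which arm is inflated more.** Let k be the 1 − KM reading and f the exit probability if nobody remitted, with Λr = −ln(1 − k) and Λx = −ln(1 − f). True incidence is Λr/(Λr + Λx) × (1 − exp(−Λr − Λx)). With f = 30% on lurasidone and 15% on NRX-101:

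- k = 40% in both arms: incidence 34.2% and 37.2%; overstated by 5.8 and 2.8 points (ratios 1.17 and 1.08).
- k = 10% and 30%: incidence 8.4% and 27.8%; overstated by 1.6 and 2.2 points (ratios 1.19 and 1.08).

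The relative overstatement is larger in the arm with more exits in both cases. The order in absolute points reverses in the second.

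**Behaviour of the tests.** In a simulation with 37 per arm, visits at Days 7, 14, 28 and 42, 3,000 runs, k = 40% in both arms and f = 72%/42%, the log-rank test with exits censored rejected in 4.8% of runs. Keeping exits at risk to Day 42 rejected in 13.7%, because cumulative remission truly differs. With f = 30%/15% the figures were 5.1% and 5.9%.

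**The case against.** Much of the opposing case stands.

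- A reader might infer that the SAP instructs censoring at exit. It does not. It is silent, and censoring is what the software does by default. Under SAP 17.1.3, where remission must hold to the end of the study, a discontinuer could even be read as a non-remitter. The defect is a missing rule.
- A reader might infer that log-rank and Cox are biased. They are not: the 4.8% rejection rate shows a valid test of the cause-specific hazard. They answer a different question from the chance of remitting.
- A reader might take the 57% failure rate implied by SAP 16.3 as the exit rate. It is back-solved rather than stated, and it covers composite treatment failure. Under SAP 17.1.2 a change in baseline medication counts as failure, and the documents do not say that every such change ends study visits. Treating every failure as a competing event would discard remissions that are still observed.
- Some exits, such as positive drug screens (SAP 12.3.4), are not clearly linked to outcome. For these the problem is missing follow-up, and the early termination visit may supply a last assessment.
- Percentages in remission are planned separately (SAP 7.4, 11.3, 17.1.4), and nothing says that the curve will be reported as that proportion.
- The trial is small. In the example of 35.0% against 41.6%, the SE of the difference is √(0.35 × 0.65/37 + 0.416 × 0.584/37) = 11.3 points, so the true gap is 6.6/11.3 = 0.6 SE and Gray's test would seldom detect it.

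These points limit the concern but do not remove it. The curve will still be displayed, with no stated treatment of exits that the trial expects to differ by arm.

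**Conclusion.** The concern holds in a limited form. SAP 20.1 and 20.2 lack a rule for discontinuation before remission, and under default censoring the Kaplan-Meier curve overstates the proportion who remit. With constant hazards and 30% to 40% true remission, the overstatement is about 4 to 15 points for exits of 20% to 40%. It is minor if exits stay below roughly 15% to 25%, depending on the remission rate. All these rates are assumptions.

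The inflation is relatively larger in the arm with more exits. The stronger claim, that it is always larger there in absolute points, needs similar remission hazards in the two arms. Nor do the documents support reading this as a threat to the trial's conclusions: the endpoint is outside the hierarchy, and the primary result and type I error are unaffected. It is a worthwhile, inexpensive improvement to a supportive analysis.

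**What to change.** Before database lock, amend SAP 20.1 and 20.2 for time to remission only:

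1. Name which remission definition (SAP 7.4, 17.1.3 or 17.1.4) the time-to-event analysis uses.
2. Treat study discontinuation before remission as the competing event, using the early termination assessment when available. Keep at risk any treatment failure who remains in visits.
3. Report Aalen-Johansen cumulative incidence to Day 42 with Gray's test. A simple alternative is to keep discontinuers in the risk set as non-remitters to Day 42.
4. Retain the planned Cox model beside it, labelled as a cause-specific hazard comparison.
5. Add a sensitivity analysis that censors exits unrelated to outcome, such as positive drug screens.

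Kaplan-Meier remains suitable for all-cause discontinuation. The cost is some SAP wording and a few lines of code, with no new data. The reported remission figure will be lower than the Kaplan-Meier reading, and counting unrelated exits as non-remission is conservative, which is why item 5 is needed.
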